3. EXPECTED RISKS/ BENEFITS

3.1 Expected Risks

Low intensity aerobic and balance exercise poses minimal risk for healthy individuals. Like all types of exercise, there is a slight risk of sustaining a musculoskeletal injury such as a sprain or strain. There is a small risk, however, when performing aerobic and balance exercises while experiencing PCS; participants may see an increase or worsening of his/her symptoms. In order to minimize this risk, exercise will begin at a very low intensity and gradually increase. All exercise sessions will be monitored by a research team member to ensure that the session is being completed at the proper intensity. Should a participant report any PCS during a session, the session will be stopped immediately. Furthermore, to ensure that participants are healthy enough to participate in exercise, all participants will be medically cleared by [name] prior to participating in the study.

There is a minor risk that, when using the driving simulator, participants may experience symptoms such as nausea or dizziness. Breaks will be allowed during the assessment in an effort to prevent this. Water will also be readily available during the assessment should the participant require it. If a participant experiences any of these symptoms and is unable to continue, the session will end.

Physical and cognitive assessment, neuroimaging, and biomarker assessment should pose minimal risk to participants.

There is a minor social risk with respect to confidentiality. This risk will be minimized by ‘de-identifying’ the personal information with codes. All names will be removed from data/samples. All data will be stored in an encrypted file on the secure Sync.com account on a password-protected computer in a locked office at LU. Any hard copies of data such as screening checklists or the IPAQ will be coded and stored in a locked filing cabinet in a secure office at LU ([name] current office, SB 1007). All saliva samples will be coded and stored in [name] secure lab.

The results of this study will be published with aggregate data, that is, data which is combined and summarized so that no individual participant can be identified.

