4.2 Study Sample Description

For the experimental group, the population being evaluate is anyone age 18-50 years, at least two weeks post injury, experiencing at least one PCS symptom that is mild in severity, as well as the remaining inclusion criteria (see attached screening checklist, Section 16.3). For the healthy control group, the population being evaluated is anyone age 18-50 years, as well as the remaining inclusion criteria (see attached screening checklist, Section 16.3)

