4.4 Participant Inclusion Criteria

A participant is eligible for inclusion in the study if the individual meets all of the following criteria:

1. Man or woman aged 18-50 years.

2. Reports at least one PCS symptom that is mild in severity.
3. It has been between two weeks and six months since date of injury.
4. Is able to provide consent in English

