After completing baseline assessments, PCS participants assigned to the AET intervention will complete an eight week supervised AET program. The program will consist of three sessions per week, approximately 40-60 minutes each. Each session will be completed under the supervision of a trainer with the Canadian Society for Exercise Physiology (CSEP-CPT) certification. At mutually agreed upon dates and times, participants will meet a member of the research team at the Sanders building, room SB-1025. Before beginning the intervention, the member of the research team will verbally restate the participant's rights and confirm that he/she is still willing to participate in the study. Participants will then be outfitted with a Polar F2 heart rate monitor, in order monitor exercise intensity during the session. Exercise intensity for each session will be based on the participant's heart rate reserve (HRR). At the first session, the participants HRR will be calculated using the Karvonen formula; Target Exercise Heart Rate = $((220 - \text{Age} - \text{Resting Heart Rate}) \times \% \text{Intensity}) + \text{Resting Heart Rate}$. Once the participant's HRR has been calculated, the participant will begin the aerobic component of the session.

The aerobic component of the session will be performed on a cycle ergometer. Participants will begin with a five minute warmup at a self selected speed, which will be used to bring the participant's heart rate to the desired intensity. Intensity for each session will start at 20% of HRR, and increase linearly by 10% for the first four weeks; at week four, participants will be cycling at an intensity of 50%. Weeks five and six will be performed at 55% of HRR, week seven will be performed at 60% of HRR, and week eight will be performed at 65% of HRR. Duration will follow a similar pattern for weeks one to four, beginning at 20 minutes and increasing in five minutes/week increments. At week five, duration will be reduced to 25 minutes, and then increase to 30 minutes for weeks six to eight.

Following completion of the aerobic portion of the session, participants will rest for five minutes before beginning the balance component of the session. Participants will perform three balance exercises (in order) each session: narrow based double leg stance, single leg stance, and tandem stance. Difficulty of these exercises will be progressively increased by modifying the

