duration, surface, and whether the participant's eyes are open or closed. For weeks one and two participants will perform the exercises with his/her eyes open; participants will perform each exercise for 15 seconds on a firm surface in week one, and on a low density foam block in week two. In weeks three and four, participants will perform the exercises with his/her eyes closed; exercises in week three will be performed on a firm surface, while week four will be performed on a low density foam block. Duration will be increased to twenty seconds per exercise for weeks three and four. Weeks four to eight will follow the same eyes open/closed and surface progression as weeks one to four; eyes open for weeks five and six, eyes closed for weeks seven and eight. Exercises will be performed on a firm surface in weeks five and seven, and on a low density foam block in weeks six and eight. Participants will perform each exercise for 35 seconds in weeks five and six, and 40 seconds in weeks seven and eight. Following the completion of the aerobic and balance components of the session, participants will complete a cool down consisting of a series of static stretches. Each session will conclude after the completion of the cooldown.

After completion of 24 sessions (eight weeks x three-one hour sessions per week), participants will repeat the procedures for the previously described baseline assessments. Similarly, HC and SC participants will complete the baseline assessments again after eight weeks.

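### The in-session stop rule in section 3.1 contradicts the risk it is meant to manage and the symptom that eligibility requires

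*Combined protocol and SAP*

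**What the plan says.** **The rule.** Section 3.1 (Expected Risks), on exercise: "Should a participant report any PCS during a session, the session will be stopped immediately". It refers to no baseline, change or severity.

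**The risk it follows.** Earlier in the same paragraph, section 3.1 describes a small risk "when performing aerobic and balance exercises while experiencing PCS; participants may see an increase or worsening of his/her symptoms". Low starting intensity, gradual progression and monitoring are given as the means of limiting it. For the driving simulator, the same section uses a two-part condition: symptoms, together with being unable to carry on.

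**Who is enrolled.** Section 4.4 makes every inclusion criterion mandatory, and one of them is "Reports at least one PCS symptom that is mild in severity". Section 4.2 describes the experimental group as "experiencing at least one PCS symptom that is mild in severity".

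**What they receive.** Section 7.2 says that "PCS participants assigned to the AET intervention will complete an eight week supervised AET program". It sets intensity, duration, surface and eye condition week by week and expects 24 sessions before reassessment. It contains no symptom baseline, symptom scale, stop rule or procedure for an interrupted session.

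**What is recorded.** Section 13 says adherence can be tracked because each intervention visit is documented on the data abstraction form. The form in 16.4 holds demographics, consent, injury and first-assessment dates, and medical history. It has no field for sessions.

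**The concern.** Two statements in one paragraph cannot both be followed. One treats exercising with symptoms as expected and worsening as the hazard; the other ends the session on a report of any PCS. Eligibility sharpens the conflict, because the AET goes only to people who had at least one such symptom when they entered.

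The rule does two jobs. It is the only symptom-based stop rule stated for the exercise sessions, and it also determines how much of the intervention is delivered. A supervisor who follows the sentence literally may stop many sessions. A supervisor who infers worsening from the context may continue in the same circumstances. Participants would then have different protection and different exposure depending on who was supervising, and the AET–SC contrast would mix effect with delivery. The plan has no auditing (13.3) and no data monitoring committee (14.7) that might notice the divergence.

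**Working it through.** The documents state no figure that depends on this rule, so the check is mainly a comparison of text.

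**1. Is the trigger tied to baseline?** No. The rule in 3.1 is set off by a report of any PCS during a session.

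**2. Can an enrolled participant meet it without getting worse?** Yes. Sections 4.2 and 4.4 require at least one mild PCS symptom at entry. If that symptom is still present and is mentioned during a session, the wording is satisfied with no change in condition. The PCS screening checklist in 16.3 omits the symptom item, but that does not remove the criterion from 4.4.

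**3. Does anything else narrow the rule?** Nothing in the documents available does. Section 7.2 is silent on symptoms during exercise. The simulator wording shows that the authors qualified a trigger elsewhere, but that qualification is not applied to exercise.

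**4. What exposure depends on the rule?** Inputs from 7.2:
- Cycling minutes per session, weeks 1 to 8: 20, 25, 30, 35, 25, 30, 30, 30. The sum is 225. The five-minute warm-up is taken as separate.
- Sessions per week: 3. Sessions in total: 8 × 3 = 24, which agrees with the protocol.
- Planned cycling: 225 × 3 = 675 minutes.

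The balance exercises follow the cycling, so 675 minutes is not the whole intervention.

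**5. How does delivery depend on the stop rate?** Let p be the probability that a session is stopped. The documents do not give p. The values below are assumptions, with p constant over weeks and sessions independent.

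| p | Expected uninterrupted sessions, 24 × (1 − p) | Chance that all 24 are uninterrupted, (1 − p)^24 | Cycling minutes in uninterrupted sessions, 675 × (1 − p) |
|---|---|---|---|
| 0 | 24 | 100% | 675 |
| 0.1 | 21.6 | about 8% | 607.5 |
| 0.5 | 12 | essentially 0 | 337.5 |
| 1 | 0 | 0 | 0 |

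A stopped session still delivers whatever was done before the stop, so expected cycling lies between 675 × (1 − p) and 675 minutes. The table shows how far delivery could move with the reading of the rule. It is not a forecast.

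**6. Is the handling of a stopped session stated?** No. Section 7.2 places AET reassessment after 24 sessions and reassessment of SC and HC after eight weeks. Section 5.1 puts reassessment of all participants after eight weeks. Neither says how a stopped session relates to the 24.

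**The case against.** The strongest reply is that the paragraph should be read as a whole. It opens with people exercising while symptomatic, names worsening as the hazard and then lists measures against that hazard, so the stop rule is naturally read as addressing symptoms provoked by exercise. On that reading this is loose drafting. The point has force: context does suggest worsening was meant. It does not remove the contradiction, because the operative sentence says something else and a safety rule should not depend on inference.

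A reader might go further and infer that the AET cannot be delivered to the people enrolled. The documents do not support that. Eligibility is judged at screening, whereas the trigger is a report during a session. A symptom may have resolved, may fluctuate or may go unmentioned. Complete non-delivery follows only as p approaches 1.

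Three further inferences also go too far:
- *A null result could not be told apart from non-delivery.* Sessions are supervised with heart-rate monitors, and section 13 says visits are documented. What stands is narrower: a visit record does not show minutes completed, and the form in 16.4 has no session fields.
- *Stopped sessions would delay AET reassessment.* Section 5.1 also fixes reassessment by the calendar, at eight weeks. What stands is that the status of a stopped session is unstated.
- *Leaving the rule out of 7.2 is an error in itself.* A rule in 3.1 about exercise sessions already governs those in 7.2. The gap matters only because 7.2 does nothing to clarify it.

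The consent materials are not in the text available, so whether they clarify the rule is unknown.

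**Conclusion.** Wrong as written: an internal contradiction. Section 3.1 conflicts with its own account of the risk and with the symptom requirement in 4.2 and 4.4, and 7.2 does not resolve it. Taken literally, the rule prevents completion of a session by an AET participant whose qualifying symptom is present and reported. It does not show that the trial is unworkable.

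The delivery at stake is 675 planned cycling minutes over 24 sessions, plus the balance work. How much would be lost is unknown, because it depends on a stop rate the documents do not give and on which reading each supervisor adopts. The conclusion itself rests on the wording and needs no assumption about that rate.

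**What to change.** 1. The investigators and responsible clinicians should reconcile sections 3.1, 4.2, 4.4 and 7.2 so that one consistent trigger applies to the exercise sessions. This review does not say what that trigger should be.
2. Add session fields to the data abstraction form in 16.4: whether the session was stopped, the reason, and the minutes completed. This would also give section 13 the adherence record it relies on.
3. State how a stopped session relates to the 24 sessions in 7.2 and to the eight-week reassessment in 5.1.

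The cost is a wording amendment with ethics review, a few fields per session, and a briefing for the session supervisors. Sample size and the planned analysis are unaffected.

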3.2 Expected Benefits

This study may directly benefit participants in the AET and SC group by potentially improving his/her PCS. This study also has benefits to the scientific community and society, in that there is scarcity of research on the effects of an AET program in individuals with PCS.

4. ELIGIBILITY

4.1 Study Setting Description

This study will be taking place at multiple sites at Lakehead University and around Thunder Bay. Participants will be recruited through the use of recruitment flyers (attached, Section 16.1) posted at various locations as well as on social media (Lakehead University School of Kinesiology Twitter and Facebook). Recruitment flyers will also be posted at Fairway Physiotherapy, as well as other local doctor's offices.

Participants will complete informed consent, screening checklist, questionnaires, ImPACT, and physical measures at the School of Kinesiology, Lakehead University.

Saliva will be collected at the School of Kinesiology, Lakehead University

Oddball and Flaker tasks will be completed at [name] Vision Laboratory, Lakehead University

The driving simulation will be completed at the Centre for Research on Safe Driving, Lakehead University

4.2 Study Sample Description

For the experimental group, the population being evaluate is anyone age 18-50 years, at least two weeks post injury, experiencing at least one PCS symptom that is mild in severity, as well as the remaining inclusion criteria (see attached screening checklist, Section 16.3). For the healthy control group, the population being evaluated is anyone age 18-50 years, as well as the remaining inclusion criteria (see attached screening checklist, Section 16.3)

4.3 Justification when a sample includes vulnerable populations or excludes certain populations

Please refer to the exclusion criteria below. Persons who have been previously diagnosed with a psychological/neurological disorder, substance abuse disorder/impairment, or are currently seeking therapy/counselling will be excluded from the study. Participants will also be excluded if he/she verbally states that he/she does not have a valid driver's license and 12 months of driving experience.

4.4 Participant Inclusion Criteria

A participant is eligible for inclusion in the study if the individual meets all of the following criteria:

1. Man or woman aged 18-50 years.

2. Reports at least one PCS symptom that is mild in severity.
3. It has been between two weeks and six months since date of injury.
4. Is able to provide consent in English

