2. OBJECTIVES / STUDY AIMS

The primary objective of our proposed study is to implement AET to reduce persistent symptoms after concussion. Our secondary objective is to investigate the usefulness of BDNF as a biomarker of persistent concussive symptoms responsiveness to AET.

Our 4 specific goals are to help people with persistent concussive symptoms by:

1. Minimizing the occurrence of persistent cognitive and physical symptoms following concussion.
2. Improving performance and efficiency of neural processing during cognitive tasks.
3. Correlating BDNF levels with severity of symptoms and correlating change in BDNF levels to improvements in physical symptoms and balance.

4. Improving functioning in activities of daily living, such as driving

RATIONALE, SIGNIFICANCE, AND JUSTIFICATION

The clinical significance, rationale, and justification of this collaborative effort is demonstrated by both clinical and research initiatives at treating people with concussion directly in our community. With the recruitment assistance by medical professionals, this project has a strong foundation and the potential to make a direct impact here in Thunder Bay. The group format of the AET is a cost- and time-effective method by which to treat a subgroup of the concussion population who experience long-lasting symptoms. This subgroup is growing as diagnostic protocols are becoming more standardized and the potential persistent effects are becoming general knowledge, especially due to increased media coverage around sport or military related injuries related to concussion. If successful, the AET protocol and salivary BDNF biomarker test may help in the assessment and treatment of persistent concussion symptoms that currently are often treated with rest and education. The findings from the proposed study will help clinicians to also monitor progress to aid in return to play, school, or work decisions, resulting in significant savings to the healthcare system and employer as a result of lost work time. Also, by improving physical health, AET may improve the quality of life.

ASSESSMENT OF OUTCOME/HYPOTHESIS

1. It is anticipated that the concussed participants receiving the AET will exhibit less mental, cognitive, and physical symptoms related to post-concussion syndrome. These signs and symptoms will be measured via the SCAT-3 and the RPSQ scores.

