5. STUDY DESIGN

5.1 Study Design

This study is designed as a randomized controlled trial. Potential PCS participants will be referred to another member of the research team by [name]. Potential participants will then complete the informed consent process and pre screening checklist. Potential healthy participants will contact the research team directly and set up a time to complete the informed consent, pre screening process, and IPAQ. After being deemed eligible based on the screening criteria (screening checklist attached, section), PCS participants will be randomly assigned to either an AET or standard of care (SC) intervention (see section 7). Using minimization software, each intervention group will be balanced by age and sex. Healthy participants will serve as the control group (HC) and will receive no treatment. Once participants in the SC group have completed the study, the AET will be offered, although it will not be included in the data analysis. Following informed consent, PCS participants will be provided with Garmin VivoSmart HR unit to monitor aerobic activity outside of the study (accelerometer, heart rate monitor, and step counter capabilities). Participants will be required to wear the Garmin units as often as possible for the duration of the study. In place of the Garmin VivoSmart HR unit, participants in the HC group will complete the IPAQ to determine physical activity levels prior to participating in the study,.

All participants will compete a series of pre and post intervention assessments (see section 7.2) over the course of one week at Lakehead University. Following the pre intervention assessments,

participants in the AET group will complete an eight week aerobic and balance retraining program at the School of Kinesiology, Lakehead University (see section 7.2). Participants in the SC group will continue with his/her standard of care for eight weeks. Healthy participants will be instructed not to significantly change his/her lifestyle (diet, physical activity) for the duration of the study weeks. After eight weeks, all participants will complete the assessments once again.

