6.4 Procedures for Participant Enrolment /Allocation /Randomization

To achieve adequate enrolment, recruitment flyers will be placed at several locations and clinics around Thunder Bay. Once informed consent has been obtained, and the potential participant has been deemed eligible through the screening process, age and sex of the participant will be used to randomly assign the participant to an intervention group through a process called minimization. This process ensures group sizes are equal and eliminates potential bias that may be introduced which is important for clinical research of small sizes. The NOSM research assistant would then communicate the enrolment and group assignment to [name] who will administer the AET intervention. The SC intervention will continue under the supervision of the participant's healthcare provider. Participants will be assigned a code number by the research assistant to ensure confidentiality is maintained during the transfer of data or samples between locations.

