11.2 Statistical Analysis

The main analysis will be a mixed factorial ANOVA to examine interaction effects between group (AET, SC, and HC) and time (pre- and post-) on measures of ERP, balance, BDNF and reaction time. If an interaction is found between group and time on any of the dependent variables (ERP, balance, BDNF and reaction time), the interaction will be explained using simple main effects. If no interaction is found for any of the dependent variable measures, the main effects for time and groups will be examined by a post hoc analysis to determine differences between groups. We anticipate greater change in the AET group compared to SC and HC group.

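### The symptom entry criterion is unclear and entry severity is neither scored before allocation nor used in minimisation or analysis, so the symptom comparison carries avoidable variance

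*Combined protocol and SAP*

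**What the plan says.** **Entry.** Section 4.4 makes its criteria conjunctive: "A participant is eligible for inclusion in the study if the individual meets all of the following criteria". The second criterion is "Reports at least one PCS symptom that is mild in severity". Section 4.2 describes the sample in nearly the same terms: "experiencing at least one PCS symptom that is mild in severity". No instrument or minimum score is given. Section 6.3 says eligibility is determined with the screening checklist. The PCS checklist in Section 16.3 covers age, English, time since injury, diagnoses, counselling and driving licence, but not symptoms. The data abstraction form in Section 16.4 has no severity field either.

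**Allocation.** Section 5.1 says "each intervention group will be balanced by age and sex", and Section 6.4 says "age and sex of the participant will be used to randomly assign the participant to an intervention group". Section 12.2 names the QMinim software and adds no further factor. Section 7.2 places the pre-intervention assessments after randomisation.

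**Objective and analysis.** Section 2 states: "The primary objective of our proposed study is to implement AET to reduce persistent symptoms after concussion". It also names the instruments: "These signs and symptoms will be measured via the SCAT-3 and the RPSQ scores". Neither scale has a row in the Section 7.1 schedule or a description in Section 7.2. Section 11.2 plans a group-by-time mixed ANOVA "on measures of ERP, balance, BDNF and reaction time", with no symptom score among the outcomes and no baseline covariate.

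**The concern.** The criterion can be read as a floor (mild or worse) or as a description of the qualifying symptom (a mild one). With no symptom item on the checklist, two screeners could apply different readings and leave no record of it.

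The second issue is statistical. How far a symptom score can fall depends strongly on where it starts. In a small trial with symptom reduction as its primary objective, entry severity is therefore an obvious variable to control, either at allocation or in the analysis. The plan does neither. Because no symptom scale is scheduled before randomisation, or anywhere in the schedule, a baseline score may not exist for later adjustment. At stake is precision, and the risk that in this one trial a difference in starting severity is mistaken for a treatment effect or hides one.

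**Working it through.** **Wording.** Section 4.4 requires every criterion to be met, and the symptom criterion in 4.2 and 4.4 carries no term such as *or greater*. Section 6.3 sends the eligibility decision to the checklist, which does not contain the criterion. The three sections do not match whichever reading was meant.

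**Inputs for the arithmetic.** The plan gives no figure for severity, so there is none to reproduce.

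- n = 20 in each of AET and SC, the two randomised arms (Sections 5.2 and 11.1), taken as stated.
- Dropout of 13% (Section 11.1), which leaves 20 × 0.87 = 17.4, about 17 completers per arm.
- Assumed: severity in SD units, equal variance before and after, severity unrelated to age and sex, and pre-post correlation r of 0.3 to 0.7. The documents give no SD, severity distribution or correlation.

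**Chance gap in baseline severity.** The SE of the AET-SC difference is sqrt(2/n) = sqrt(2/20) = 0.316 SD. The chance of a gap larger than t in either direction is 2 × (1 − Φ(t/0.316)):

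- t = 0.3: z = 0.949, probability 34%
- t = 0.5: z = 1.58, probability 11%
- t = 0.75: z = 2.37, probability 2%

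With 17 per arm the SE is sqrt(2/17) = 0.343, and the chance of a gap above 0.5 SD is about 15%.

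**Effect on an unadjusted change contrast.** With two time points, the AET-SC part of the group-by-time interaction compares mean changes. If the arms start D apart and treatment does nothing, the expected gap afterwards is r × D. The contrast in change is then shifted by (1 − r) × D in size, and the arm that starts worse appears to improve more.

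**Variance that adjustment would remove.** The SD of change is sqrt(2(1 − r)). The residual SD after adjusting for baseline is sqrt(1 − r²). The variance ratio, adjusted to unadjusted, is (1 − r²)/(2(1 − r)) = (1 + r)/2, ignoring the small cost of estimating the slope.

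| r (assumed) | Shift from a 0.5 SD gap | SD of change | Residual SD, adjusted | Variance ratio |
|---|---|---|---|---|
| 0.3 | 0.5 × 0.7 = 0.35 SD | 1.18 | 0.95 | 0.65 |
| 0.5 | 0.5 × 0.5 = 0.25 SD | 1.00 | 0.87 | 0.75 |
| 0.7 | 0.5 × 0.3 = 0.15 SD | 0.77 | 0.71 | 0.85 |

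Adjustment therefore removes 35%, 25% or 15% of the variance of the unadjusted change contrast.

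**The case against.** The best case for the plan has four parts.

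*The intended meaning is clear.* A floor of mild is the natural reading. A reader might infer that people with only moderate or severe symptoms are shut out. The literal wording allows that, but it is almost certainly a drafting slip, and the checklist has no item that would enforce it. This part of the objection stands. What remains is the need to make the sections agree.

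*A clinician sees candidates first.* Section 3.1 requires medical clearance, Section 6.1 has referrals forwarded if appropriate, and the first budget note in Section 16.6 allows 15 minutes of physician evaluation for each of 80 candidates. Section 4.2 can also be read as leaving only the other criteria to the checklist. Together with the term *PCS symptom*, this answers the inference that a headache or tiredness pre-dating the injury would simply qualify, and with it the inference that the BDNF-severity hypothesis is confounded. It does not supply a recorded severity score.

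*Chance imbalance is not a defect of randomisation.* This is correct. The probabilities above apply to any unstratified covariate at this sample size, the estimate is unbiased on average, and the ordinary standard error already reflects the variation. The point is only that some of this variance is avoidable, for an obvious prognostic variable, at almost no cost.

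*A low entry threshold is a legitimate choice.* This also stands. A reader might infer that someone entering with one mild symptom cannot show benefit, and scale the expected effect down by the share of such entrants. That person can still lose the symptom, which is an improvement. The documents give no severity distribution from which to derive a share. A symptom floor also does not directly limit the ERP, balance, BDNF or reaction-time outcomes in Section 11.2.

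**Conclusion.** The point holds in a limited form. The entry wording and the checklist must be reconciled. Separately, entry severity is controlled neither at allocation nor in the analysis, which costs precision on the trial's primary objective. The gap probabilities rest on 20 per arm and on severity being unrelated to age and sex; if it is related, the existing minimisation already removes some of the gap. The shifts and variance ratios rest on assumed correlations and equal variances. They apply if symptom scores are analysed by unadjusted change, as the Section 11.2 model would do; that section does not at present list a symptom outcome. None of this shows that the treatment estimate is biased, that moderate or severe cases would in practice be excluded, or that mildly affected entrants contribute nothing. It is worth changing before enrolment, but it does not invalidate the design.

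**What to change.** 1. Reconcile Sections 4.2, 4.4 and 16.3 so that the symptom criterion reads the same in each, states whether mild is a minimum, and appears on the PCS checklist. Which threshold is right is for the investigators to decide.
2. Administer one of the scales named in Section 2 (SCAT-3 or RPSQ) at the existing screening visit, after consent and before randomisation. Participants are unblinded (Section 12.3), so this also gives a baseline reported before they know their group.
3. Enter that score in QMinim as a third factor with age and sex, with any categories fixed in advance.
4. Adjust the AET-SC symptom comparison for the screening score, as in ANCOVA. This presupposes that the same scale is repeated after eight weeks and that Sections 7.1 and 11.2 list it.

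Adjustment alone would deal with most of the imbalance, but it too needs the score from step 2. The cost is a few minutes of self-report per candidate, an ethics-board amendment, and slightly looser balance on age and sex with three factors in 40 randomised participants. No extra visit is needed and eligibility need not be narrowed. In particular, a requirement that symptoms be new or worse since injury is not needed for this point, and it would restrict recruitment where the budget already expects to screen 80 people to reach 40.
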